#### **8.3 Protocol Deviations**

A major deviation will be defined as participants enrolled and randomized but did not meet eligibility criteria during the course of the study, or any deviations that affect safety or overall data integrity, particularly if it relates to study endpoints. The number of participants in each protocol deviation category listed below will be summarized by analysis set and treatment group. Individual participants will appear in a listing.

Possible protocol deviations include the following categories:

- Participant entered study but did not meet criteria
- Participant developed withdrawal criteria but was not withdrawn
- Participant received excluded concomitant treatment
- Protocol procedure not performed per protocol
- Participant received incorrect treatment or incorrect dose
- Protocol procedure performed out of range
- Miscellaneous

#### 8.4 Baseline Values

Baseline values are from Baseline Visits for all measures, except C-SSRS, AUDIT, DUDIT, resting blood pressure (BP), Body Mass Index (BMI). For C-SSRS, the initial screening visit will be conducted with the 'Lifetime' version of the measure. The Independent Rater Screening assessment of 'Since Last Visit' suicidal ideation and behavior will be used as 'Baseline.' For the AUDIT and DUDIT measures and resting BP, BMI, results collected at Screening will be used as the Baseline value.

## 8.5 Participant Disposition and Dosing Summary

The Safety Set will be included in the summary of participant disposition and accountability. The number and percent of participants who completed or discontinued the study will be displayed with reasons for early termination, where the percent is with respect to the total number of participants. The timepoint of doses and total MDMA (mg) administered will be summarized for the Safety Set.

#### 8.6 Demographics and Baseline Characteristics

Participant demographic data and Baseline characteristics will be summarized descriptively. The demographic data and baseline characteristics will be summarized for the Safety Set and overall.

#### 8.7 Effectiveness Analyses

For all primary, secondary, and exploratory endpoints descriptive statistics (n, mean, standard deviation, median, range, or counts and percentages where appropriate) will be provided. Longitudinal CAPS-5 Total Severity Score and SDS item scores will be plotted across visits to characterize the onset of treatment effect.

#### 8.7.1 Primary Effectiveness Analyses

The *de jure* estimand of treatment effectiveness will be used to estimate the change in CAPS-5 score from baseline due to MDMA-assisted psychotherapy on PTSD symptom severity in the intended population of patients with PTSD from any cause. The primary estimator of effectiveness will be the mean change in CAPS-5 Total Severity Scores from Baseline to 18 weeks after start of dosing (Visit 19). Least squares means from a restricted maximum likelihood (REML)-based mixed model for repeated measures (MMRM) will be used to estimate the change in CAPS-5 from baseline to each visit. CAPS-5 data collected after treatment discontinuation will not be included in the *de jure* estimand. Missing data will not be imputed.

## 8.7.2 Key Secondary Effectiveness Analyses

For the key secondary analysis of effectiveness, the *de jure* estimand will be used to estimate the change from baseline due to MDMA-assisted psychotherapy on PTSD on the SDS in the intended population of patients with PTSD from any cause. The SDS is a 3-item scale measuring the severity of disability in the domains of work, family life/home responsibilities and social/leisure activities. Each of these three domains is scored on a tenpoint Likert scale, where a score of 0 is 'not at all impaired', 5 is 'moderately impaired' and 10 is 'very severely impaired'. For each study participant at each visit, the responses on the 3 items of the SDS will be summarized with a mean. In cases where the response on item 1 is not applicable, it will not be considered missing data. Thus, missing data assumptions and methodologies are not required when item 1 is not answered. Whereas when all 3 items have a response, the summary measure is the mean of the 3 item responses, in the cases where item 1 is not answered the summary measure will consist of the mean of items 2 and 3. It is expected that no more than 20% participants will have not have an applicable score for item 1, based on prior studies of paroxetine with PTSD. To limit missing data and ensure standardized administration, the SDS will be administered in a clinician-rated format during the same visits as the CAPS-5 by the centralized Independent Rater Pool.

A secondary estimator of effectiveness will be the mean change in SDS Mean Scores from Baseline to 18 weeks after start of dosing (Visit 19). Least squares means from a restricted maximum likelihood (REML)-based mixed model for repeated measures (MMRM) will be used to estimate the change from baseline to each visit. SDS data collected after treatment discontinuation will not be included in the *de jure* estimand. Missing data will not be imputed and will be considered missing at random.

## **8.7.3 Exploratory Analyses**

[figure not shown]
Post-hoc exploratory analyses not identified in this SAP may be performed to further examine the study data. These analyses will be clearly identified as such in the final clinical study report.

In exploratory analyses, additional baseline covariates (age, gender, ethnicity, index trauma, complexity and severity of trauma, medication tapering, diagnosis of comorbid depression, diagnosis of comorbid Axis 2 diagnosis, adverse childhood experiences) may be assessed for inclusion in the model at a p<0.05. One-group pretest-posttest Cohen's *d* effect size will be estimated.

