4.2 Exclusion Criteria

Potential participants are ineligible to enroll in the protocol if they:

- 1. *Are not able to give adequate informed consent
- 2. Are currently engaged in compensation litigation whereby financial gain would be achieved from prolonged symptoms of PTSD or any other psychiatric disorders
- 3. Are likely, in the investigator's opinion and via observation during the Preparatory Period, to be re-exposed to their index trauma or other significant trauma, lack social support, or lack a stable living situation

- 4. Have used Ecstasy (material represented as containing MDMA) more than 10 times within the last 10 years or at least once within 6 months of the first Experimental Session; or have previously participated in a MAPS-sponsored MDMA clinical trial
- 5. Have any current problem which, in the opinion of the investigator or Medical Monitor, might interfere with participation

Psychiatric History

- 6. *Have received Electroconvulsive Therapy (ECT) within 12 weeks of enrollment
- 7. *Have a history of, or a current primary psychotic disorder, bipolar affective disorder type 1 assessed via MINI or dissociative identity disorder assessed via DDIS
- 8. *Have a current eating disorder with active purging assessed via MINI
- 9. *Have current major depressive disorder with psychotic features assessed via MINI
- 10. *Meet DSM-5 criteria for active substance use disorder for any substance other than caffeine or nicotine in the past 60 days assessed via MINI, AUDIT, DUDIT, drug test, and blood %carbohydrate-deficient transferrin (%CDT)
- 11. Have current Personality Disorders Cluster A (paranoid, schizoid, schizotypal), Cluster B (antisocial, borderline, histrionic, narcissistic), or Cluster C (avoidant, dependent, obsessive-compulsive) assessed via SCID-5-PD. Diagnoses will be confirmed via clinical interview
- 12. Any participant presenting current serious suicide risk, as determined through psychiatric interview, responses to C-SSRS, and clinical judgment of the investigator will be excluded; however, history of suicide attempts is not an exclusion. Any participant who is likely to require hospitalization related to suicidal ideation and behavior, in the judgment of the investigator, will not be enrolled
- 13. Would present a serious risk to others as established through clinical interview and contact with treating psychiatrist

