8.1.2 Independent Rater Screening

If participants meet initial eligibility during Screening, an IR will continue the eligibility assessment via telemedicine after reviewing the results of the LEC-5 and SCID-5-SPQ. The IR interview may be recorded to assess reliability of ratings. If possible, the potential participant should be present at the study site during this assessment, in case the therapy team is needed for support. If a participant reports suicidal ideation during this assessment, the IR will contact the therapy team after the call and present any concerns. The therapy team will follow-up with the participant to ensure safety, provide support, recommend treatment, or schedule a visit to the study site.

- Using the results of the SCID-5-SPQ to guide the interview, the IR will perform the SCID-5-PD to assess Axis 2 personality disorders. Only appropriate modules will be completed.
- The IR will also ask relevant questions from the DDIS to identify dissociative disorders and administer the Since Last Visit C-SSRS to determine suicidal risk.
- The IR will complete MINI interview to assess Axis I psychiatric disorders.

The results from the MINI, SCID-5-PD, DDIS, and C-SSRS will be provided to the therapy team at the site to review along with all other Screening information to determine eligibility. Items assessed by the IR at this visit will be confirmed in the Preparatory Period by clinical observation, but the measures will not be repeated. If site staff deem the participant eligible, schedule Enrollment (Visit 0).

If the results of the any measure or interview indicate a diagnosis is present, the investigator is not permitted to use their clinical judgment to deny the diagnosis. However, if a diagnosis is not present or uncertain according to any measure or interview, but the investigator believes the participant presents with a particular disorder, they may diagnose and deem the participant ineligible if appropriate.

After the initial screening visit the IRs will be blinded to visit number, number of treatments received and any study data for the participant. IR visits will be assigned based on availability.

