14.1.1.3 Exploratory Analyses

One-group pretest-posttest Cohen's *d* effect size will be estimated. Exploratory sub-group analyses may be conducted when possible to evaluate effects and by individual demographic characteristics (e.g. age, gender, ethnicity, index trauma, dissociative subtype of PTSD, presence of secondary traumatic stressors during the assessment period with LEC-5, medication tapering, diagnosis of comorbid depression, diagnosis of comorbid Axis 2 diagnosis, and number of experimental sessions completed). Post-hoc exploratory analyses not described in the protocol or Statistical Analysis Plan may be performed to further examine the study data. These analyses will be clearly identified as such in the final clinical study report.

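### Admitting exploratory covariates to the model only at p<0.05 exaggerates weak and moderate associations and makes the adverse-childhood-experiences objective depend on significance

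*SAP*

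**What the plan says.** **Covariates.** SAP 8.7.3 names nine baseline candidates: age, gender, ethnicity, index trauma, complexity and severity of trauma (counted here as one), medication tapering, comorbid depression, comorbid Axis 2 diagnosis, and adverse childhood experiences. The entry rule is "diagnosis of comorbid Axis 2 diagnosis, adverse childhood experiences) may be assessed for inclusion in the model at a p<0.05". No selection procedure and no multiplicity adjustment are given. SAP 8.0 makes all tests other than the primary one two-sided at 0.05.

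**Adverse childhood experiences (ACE).** Protocol 3.4 and SAP 3.4 each list the effect of ACE on the CAPS-5 analyses as an exploratory objective. Protocol Table 4 plans ACE as a covariate.

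**Subgroups.** Protocol 14.1.1.3 has its own list of ten example factors. They are optional: "Exploratory sub-group analyses may be conducted when possible". The list ends with "diagnosis of comorbid Axis 2 diagnosis, and number of experimental sessions completed". Sessions completed is not in the SAP 8.7.3 list.

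**Eligibility.** Exclusion 11 in Protocol 4.2 bars people who "Have current Personality Disorders Cluster A (paranoid, schizoid, schizotypal), Cluster B (antisocial, borderline, histrionic, narcissistic), or Cluster C (avoidant, dependent, obsessive-compulsive) assessed via SCID-5-PD". Where a measure shows a diagnosis, Protocol 8.1.2 says "the investigator is not permitted to use their clinical judgment to deny the diagnosis".

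**Data after stopping treatment.** SAP 8.7.1: "CAPS-5 data collected after treatment discontinuation will not be included in the *de jure* estimand". Protocol 5.3.4 keeps collecting the assessments from people who stop treatment but stay in the study, and SAP 8.2 puts those data into a supportive *de facto* analysis. Neither document names the estimand for the subgroup analyses.

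**The concern.** A covariate that enters only when significant is reported only when its estimate happens to be large. In a small study this does two things: some null covariates get in, and real but modest ones appear larger than they are. The study is a lead-in meant to inform later work, so the size of these associations is what the exploratory section is for.

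ACE is the clearest case. Both documents set its effect as an objective, yet under SAP 8.7.3 it stays in the model only if p<0.05. A near-zero or imprecise ACE estimate would be informative, and the rule does not secure its reporting.

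Two list entries also sit badly with the rest of the plan. A comorbid Axis 2 diagnosis is named as a covariate and as a subgroup although current personality disorders are excluded. Participants with fewer than three sessions have, by definition, stopped treatment before Visit 19, where the *de jure* rule discards their CAPS-5.

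**Working it through.** The plan gives no figure to reproduce on this point: SAP 7.0 states that no sample size or power calculation was made. The one related figure checks: 8/107 = 7.48%, stated in Protocol 2.2.4 as 7.5%.

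**1. False entry.** Inputs: nine covariates, two-sided 0.05, one test each, independence assumed.
- All nine: 1 − 0.95^9 = 37.0%; expected false entries 9 × 0.05 = 0.45.
- Without Axis 2: 1 − 0.95^8 = 33.7%; expected 8 × 0.05 = 0.40. Simulation with eight null covariates gave 33%.

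Removing Axis 2 therefore barely changes the problem. Correlated covariates would lower these figures; stepwise searching or several codings per covariate would raise them.

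**2. Exaggeration.** The smallest correlation that reaches p<0.05 is t/√(t² + n − 2), with t the two-sided critical value.
- n = 60: t = 2.002, so 2.002/√(4.007 + 58) = 0.25.
- n = 30: t = 2.048, so 2.048/√(4.196 + 28) = 0.36.

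A true correlation of 0.20 can be kept only when it is estimated above these values. Simulation (standardised continuous covariate, one outcome, 20,000 replicates) gives the average. The correlations and the two sample sizes are assumptions; the documents fix only the maximum of 60.

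| True correlation | n = 60: chance kept | n = 60: mean absolute slope if kept (factor) | n = 30: chance kept | n = 30: mean absolute slope if kept (factor) |
|---|---|---|---|---|
| 0.1 | 11% | 0.316 (3.2) | 8% | 0.440 (4.4) |
| 0.2 | 34% | 0.337 (1.7) | 19% | 0.450 (2.3) |
| 0.3 | 65% | 0.368 (1.2) | 37% | 0.470 (1.6) |
| 0.5 | 99% | 0.504 (1.0) | 83% | 0.546 (1.1) |

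**3. Effect on the mean change.** With eight null covariates, centred and with complete data, entering those that passed moved the adjusted mean change by nothing beyond rounding error. Its standard error fell by 1.5% (n = 60) or 3.1% (n = 30). Coverage of the 95% interval was 94.5% and 94.1%, against 94.9% with no selection.

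**4. Axis 2.** Exclusion 11 names ten current disorders across Clusters A to C, and a positive finding cannot be waived. By design, the expected number with a current disorder is 0. Only a deviation, a past disorder or a disorder outside the ten could fill the level.

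**5. Sessions completed.** Assume everyone who stops early has fewer than three sessions. At the 5% early termination expected in SAP 8.2, 60 × 0.05 = 3.0. At the earlier dropout rate, 60 × 8/107 = 4.5. At N = 60 and 5%, the chance of none is 0.95^60 = 4.6% and the chance of five or more is 18%. Under *de jure* these participants have no Visit 19 values, though values at Visits 8 and 13 obtained before stopping still count. Under *de facto* they can have Visit 19 values.

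**The case against.** The best defence is that SAP 1.0 defines exploratory analyses as a search for trends that may suggest hypotheses, that both lists are optional, and that no confirmatory claim depends on them. That stands and limits the weight of the point. It does not make a selected estimate unbiased, and it does not explain why a stated objective should depend on a p-value.

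Several stronger readings are tempting, and the documents do not support them.
- *The trial's effect estimate is distorted.* It is not: step 3 shows no shift and only a small loss of coverage.
- *Every covariate that surfaces is overstated.* The factor is 1.0 at a correlation of 0.5 and n = 60. The problem lies with weak and moderate associations.
- *The Axis 2 level can hold only protocol violators.* The exclusion says current; the analysis lists do not, and psychiatric history is collected. The level is empty or nearly so, and an optional analysis with an empty level would simply be skipped.
- *The sessions split is empty.* That follows only if the *de jure* rule is applied at Visit 19. Protocol 14.1.1.3 names no estimand, and in the planned *de facto* analysis the group is small, not absent.
- *Selected covariates will be carried into Phase 3 models.* The documents link this study to Phase 3 through power assumptions, the CAPS-5, reproducibility and therapist supervision, and do not mention covariate choice.

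**Conclusion.** The entry rule in SAP 8.7.3 is a real but minor weakness. It carries up to a 37% chance of at least one null covariate entering, if the tests are independent. It overstates kept coefficients by about 1.7 times at a true correlation of 0.2 and n = 60, more for weaker associations or fewer participants, and hardly at all for strong ones. These factors rest on assumed correlations, continuous covariates and one test per covariate. The rule also leaves the ACE objective conditional on significance. The primary mean change is not biased.

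The Axis 2 entry and the sessions split are housekeeping. The first conflicts with exclusion 11 but changes no result. The second lacks a stated estimand and will rest on about 3 to 4.5 of 60 participants.

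**What to change.** Replace the p<0.05 entry rule in SAP 8.7.3. Fit each listed covariate once and report every estimate with its 95% confidence interval whatever its p-value, labelled exploratory. This needs only SAP wording and no new data; the one downside is a longer table.

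Housekeeping:
- Remove comorbid Axis 2 diagnosis from SAP 8.7.3 and Protocol 14.1.1.3, or redefine it, for example as a past disorder. Do not substitute a SCID-5-SPQ score: the documents describe that questionnaire only as a screening aid to the interview and define no score for analysis.
- If the Protocol 14.1.1.3 split by sessions completed is run at Visit 19, say that it uses the *de facto* data and present it descriptively, with the group sizes shown.

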# 8.7.4 Responder Analyses

The CAPS-5 produces a Total Severity Score based on severity of PTSD symptom domains described in the DSM-5, as well as a categorical rating indicating whether a participant meets PTSD diagnostic criteria. A psychometric validation study found the following severity score ranges for the CAPS-5: Asymptomatic (0-10), Mild (11-22), Moderate (23-34), Severe (35-46), Extreme (47+). Based on these data, a 10-point reduction in CAPS-5 Total Severity Score is clinically meaningful. As an alternate definition of treatment response to assess clinical significance of study outcomes, the sponsor will conduct a responder analysis to support findings from the primary effectiveness analysis, and to explore how many single-dose treatments are needed to achieve response (See Figure 1).

## Figure 1: CONSORT for PTSD Responder Analysis After Treatment

 Response at T2, T3, and T4 will be in comparison to Baseline at T1.

# 8.8 Safety Analyses

Safety assessment analyses for this study will include summaries of unsolicited adverse events, concomitant medications, suicidal ideation and behavior, and vital signs. Qualitative safety analyses will examine safety data with summary tables listing drug exposure, concomitant medications/therapies, unsolicited AEs, and percentages tabulated.

## 8.8.1 Analysis of Exposure

The frequencies and percentages of participants with exposure will be summarized. Data will be tabulated for the Safety Set.

## 8.8.2 Analysis of Adverse Events

The primary measure of safety will be the reporting of unsolicited AEs. All AEs collected from Enrollment to Termination will be categorized as follows:

- Pretreatment AEs are defined as AEs that occur during the Preparatory Period prior to the first dose in the first Experimental Session
- Treatment Emergent AEs are defined as AEs that occur during the Treatment Period from the first Experimental Session to the last Integrative Session
- AEs that occur on and two days after MDMA or placebo administration
- AESIs are defined as AEs specified in the protocol related to cardiac function and abuse liability
- Follow-up Period AEs are defined as AEs that occur during the Follow-up Period after the last Integrative Session through Termination
- AEs leading to discontinuation of IP
- AEs resulting in death or hospitalization.
- SAEs
- AEs continuing at Termination.

Verbatim terms on case report forms will be mapped to preferred terms (PT) and system organ class (SOC) using the Medical Dictionary for Regulatory Activities (MedDRA) Version 17.0. Frequency and incidence of AEs will be displayed by PT, sorted by SOC, and summarized by treatment group, analysis set, category (as defined above), severity, and seriousness. AEs will be analyzed and presented as follows:

- If a participant has more than one AE mapped to the same PT, that AE will be reported once using the highest severity
- Relationship will be determined based on relative incidence of TEAEs with at least twofold difference between MDMA vs. placebo
- Compare relative incidence of AEs during Experimental Sessions such as clinical signs and symptoms, such as chest pain, shortness of breath, or neurological symptoms or any other signs or symptoms that may be indicative of a medical complication of the investigational product
- AEs that occur on day of Experimental Sessions and two days after IP administration will be presented separately.

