9.1.2 Dose Modifications

In the first Experimental Session, the initial dose will be 80 mg MDMA. In the second and third Experimental Sessions, the initial dose may be increased to 120 mg MDMA unless contraindicated. The choice of whether to keep the dose the same or change it from the first Experimental Session will be made by the therapy team in consultation with the site physician based on observed response, tolerability to the previously administered dose, and discussion with the participant. In each Experimental Session, 1.5 to 2 hours after the initial dose is given, the participant will be administered a supplemental half-dose unless contraindicated.

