10.2.2.1 Cardiovascular and Cerebrovascular Risks and Mitigation

MDMA is known to transiently increase heart rate and blood pressure in a dose-dependent manner that is generally not problematic for physically healthy individuals. These changes should last no more than 8 hours. Participants with PTSD in MAPS-sponsored Phase 2 studies do not appear to differ from healthy individuals in this sympathomimetic, physiological response. Most people do not experience elevations in cardiovascular parameters that exceed those seen after moderate exercise. An examination of safety data drawn from Phase 2 studies of MDMA-assisted psychotherapy detected a dose-dependent increase in systolic blood pressure but not diastolic

blood pressure. Characterization of sympathomimetic effects among participants with controlled hypertension is ongoing.

Risks posed by elevated blood pressure will be addressed by excluding people with pre-existing uncontrolled hypertension and monitoring blood pressure and pulse, as described in Section 4.2 Exclusion Criteria. Before and after IP administration in Experimental Sessions, the therapy team will monitor vital signs. The therapy team will attend to clinical signs and symptoms during Experimental Sessions, such as chest pain, shortness of breath, neurological deficit or confusion other potential indicators of end organ effects of hypertension that prompt additional vital sign measurements, and intervene if appropriate. The therapy team will notify the site physician for evaluation if this occurs. If any participant has neurological deficits, as assessed by the site physician, whether or not they are associated with hypertensive crisis, they will be monitored, as described above, for rare complications of cardiovascular effects, such as stroke or acute myocardial infarction (AMI). If a participant experiences ischemic type chest pain, whether or not it is associated with hypertensive crisis, they will be given 0.4 mg of sublingual nitroglycerin every 5 minutes as needed for chest pain pending transport to the hospital. If evaluation at the hospital reveals a nonhemorrhagic stroke, there will be sufficient time to administer recombinant tissue plasminogen within the 3-hour time frame recommended in the American Academy of Neurology/American Heart Association guidelines [111, 112].

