14.1.2 Safety Analyses

Safety data will be summarized by exposure to IP, unsolicited AEs, concomitant medications, suicidal ideation and behavior, and vital signs overall. If a participant has more than one AE mapped to the same PT, that AE will be reported once using the highest severity. AEs that occur on Day 0 (Experimental Session), Day 1, Day 2 after IP administration will be presented separately. Report incidence of AEs during Experimental Sessions such as clinical signs and symptoms, such as chest pain, shortness of breath, or neurological symptoms or any other signs or symptoms that may be indicative of a medical complication of the IP.

Frequency and incidence of concomitant medications will be displayed by generic name, sorted by class, and summarized by analysis set and category. Concomitant medications taken on Day 0 (Experimental Session), Day 1, Day 2 after IP administration will be presented separately. Any psychiatric concomitant medications will be tabulated by period (Preparatory, Treatment Period, Follow-up Period). Frequency and incidence of positive or serious ideation and suicidal behavior will be presented using descriptive statistics of C-SSRS scores in tabular format. Vital signs (heart rate, blood pressure, and body temperature) for Experimental Sessions will be summarized using descriptive statistics in tabular format listing values at pre-IP administration, prior to the supplemental dose, and at the end of each Experimental Session. Additional details are available in the Statistical Analysis Plan.

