# 2.0 Introduction

This document contains a Statistical Analysis Plan (SAP) for MP16, "An Open-Label, Multi-Site Phase 2 Study of the Safety and Effect of Manualized MDMA-Assisted Psychotherapy for the Treatment of Severe Posttraumatic Stress Disorder."

MP16 tests a flexible dosing regimen of 80mg MDMA in Session 1, and 80mg or 120mg MDMA in Sessions 2 and 3, each followed by a supplemental half-dose.

The Multidisciplinary Association for Psychedelic Studies (MAPS) is a non-profit research and educational organization working to obtain approval for the prescription use of 3,4methylenedioxymethamphetamine (MDMA) in conjunction with psychotherapy in persons with posttraumatic stress disorder (PTSD). MAPS has delegated trial organization activities to its wholly owned subsidiary, MAPS Public Benefit Corporation (MPBC).

This open-label Phase 2 study will serve as a lead-in to the sponsor's two planned Phase 3 studies, only sites planned for Phase 3 will participate in these studies. This open-label lead-in Phase 2 study will serve to validate assumptions made for statistical power calculations supporting planned Phase 3 clinical trials and will provide data on the updated version of the instrument for the Primary Outcome measure, the Clinician Administered PTSD Scale for DSM-5 (CAPS-5), which will be used in Phase 3. In addition, this study will gather supportive data on the safety and effectiveness of manualized MDMA-assisted psychotherapy while providing an opportunity for clinical supervision to planned Phase 3 therapy teams. This study will be the sponsor's first multi-site studies of MDMA-assisted psychotherapy for PTSD and will explore reproducibility of findings in a multi-site format to confirm the Phase 3 study design.

This version 2 of the Statistical Analysis Plan was modified from version 1. The changes made include the following, 1) separate plans were made for each individual study, MP16 and MP17; 2) analyses were modified to be within-subject and not comparison between studies; and 3) doses used in each study were updated.

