## 8.8.5 Summary of Vital Signs

Vital signs (heart rate, BP, and body temperature) for Experimental Sessions will be summarized using descriptive statistics in tabular format listing values at pre-IP, prior to the supplemental dose, and at the end of each Experimental Session. Change from Baseline in vital signs will be presented.

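### No planned safety table is split by the dose given at the session, although initial doses at Sessions 2 and 3 can be 80 mg or 120 mg

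*SAP*

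**What the plan says.** **Dose.** SAP 2.0 states that "MP16 tests a flexible dosing regimen of 80mg MDMA in Session 1, and 80mg or 120mg MDMA in Sessions 2 and 3"; a half-dose is added at every session. Protocol Table 3 gives 80 to 120 mg in total for Session 1 and 80 to 180 mg for each later session. Under Protocol 9.1.2 the later dose is chosen "based on observed response, tolerability to the previously administered dose, and discussion with the participant". SAP 6.0 and 7.0 confirm one arm and no randomisation.

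**Safety tables.**
- Adverse events (SAP 8.8.2) are "summarized by treatment group, analysis set, category (as defined above), severity, and seriousness". Each preferred term is counted once per participant, at its worst severity.
- Concomitant medications (8.8.3) are broken down by treatment group, analysis set and category.
- C-SSRS results (8.8.4) are broken down by treatment group and time period, including before and after dosing at each session.
- Vital signs (8.8.5) are tabulated "listing values at pre-IP, prior to the supplemental dose, and at the end of each Experimental Session".
- Protocol 14.1.2 states: "Safety data will be summarized by exposure to IP, unsolicited AEs, concomitant medications, suicidal ideation and behavior, and vital signs overall".

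**Exposure.** SAP 8.8.1: "The frequencies and percentages of participants with exposure will be summarized". SAP 8.5 adds that the timing of doses and "total MDMA (mg) administered will be summarized for the Safety Set".

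**Related text.** Protocol 14.1 asks for descriptive statistics both overall and by initial dose received, but for outcome measures. Protocol 10.2.2.1 reports that an examination of earlier Phase 2 safety data "detected a dose-dependent increase in systolic blood pressure but not diastolic" pressure.

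**The concern.** Dose is the one exposure that varies by design in this trial, and the plan does not set harms against it. The factor that it names, treatment group, separates nothing in a one-arm study. It reads as a carry-over from the earlier joint plan for MP16 and MP17, as does the rule in SAP 8.8.2 that judges relatedness by comparing MDMA with placebo. MP16 has no placebo, and Protocol 11.1 does not collect the investigator's opinion on relatedness for non-serious events.

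The safety objective (Protocol 3.3) is to support the package insert. A pooled incidence describes the mix of doses that the sites happened to choose. It does not describe sessions at either dose. The plan is also uneven: Protocol 14.1 describes benefit by initial dose, while harm is not described that way, and blood pressure, for which the protocol itself reports a dose relation, is pooled across doses at Sessions 2 and 3.

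**Working it through.** The documents give no figure on this point to reproduce, so the check is of the planned tables, followed by an illustration.

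**1. Is any safety table split by dose?**

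| Domain | Planned breakdown | Split by session? | Split by dose? |
|---|---|---|---|
| Adverse events (SAP 8.8.2) | treatment group, analysis set, category, severity, seriousness | no | no |
| Medications (8.8.3) | treatment group, analysis set, category | no | no |
| C-SSRS (8.8.4) | treatment group, time period | yes | no |
| Vital signs (8.8.5) | time point within session | yes | no |

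**2. Does the by-dose rule in Protocol 14.1 reach safety?** No. Protocol 7.0 lists outcome and safety measures as separate classes, Protocol Table 4 types the C-SSRS as a safety measure, and SAP 1.0 confines outcome measures to the primary and secondary ones.

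**3. How many sessions are affected?** With N up to 60 there are at most 3 × 60 = 180 sessions. Session 1 supplies 60, all with an 80 mg initial dose. Sessions 2 and 3 supply 2 × 60 = 120, in a dose mix that the documents do not predict. By-session tables therefore isolate the 80 mg initial dose at Session 1 only. Comparing Session 1 with later sessions confounds dose with order.

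**4. Do the exposure tables fill the gap?** The percentage exposed within the Safety Set is 100% by definition, because the set consists of those who received any drug. Total mg is partly informative. If it is reported per session, 120 mg is ambiguous (80 + 40, or 120 alone). If it is reported only as a three-session total, more is lost: listing Session 1 as {80, 80+40} and Sessions 2 and 3 as {80, 80+40, 120, 120+60}, a total of 320 mg arises from 8 dose paths and 360 mg from 4. SAP 8.5 does not say which is meant. Neither form is crossed with harms.

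**5. Illustration. The risks and the shares on 120 mg are assumptions.** Take a per-session risk of 10% at 80 mg and 30% at 120 mg, with 60 participants at a later session.

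Pooled rate = (n80 × 0.10 + n120 × 0.30) / 60.

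Power of a two-sided 0.05 comparison = Φ[(0.20 − 1.96 × SE0) / SE1], where SE0 uses the pooled rate and SE1 the separate rates.

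| Share on 120 mg | n80 / n120 | Pooled rate | Power, 10% v 30% |
|---|---|---|---|
| 50% | 30 / 30 | (3 + 9)/60 = 20% | about 49% |
| 75% | 15 / 45 | (1.5 + 13.5)/60 = 25% | about 30% |
| 90% | 6 / 54 | (0.6 + 16.2)/60 = 28% | about 10% |

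The adverse event tables count participants. If sessions were also independent, the same risks would give 1 − 0.9³ = 27.1% on path 80-80-80 and 1 − 0.9 × 0.7² = 55.9% on path 80-120-120. The planned figure would fall between these, according to how many participants moved to 120 mg. Independence within a participant is doubtful, so these two figures show direction only.

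**The case against.** The strongest reply is that the summary fits the question. Protocol 5.5 says that flexible dosing was chosen to resemble expected clinical practice, and none of the 11 safety objectives asks for a dose contrast. Incidence under the regimen as used is a legitimate quantity. That stands, and it is why an overall column should stay.

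The second reply is that a by-dose table could mislead. Later doses depend partly on how the earlier dose was tolerated, so participants kept at 80 mg may be those who tolerated it poorly. This can mask or reverse a true dose difference. The power figures also show that such a table could not reliably separate the doses. Both points stand, and they limit the table to description.

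Third, end-of-session vital signs may show little by dose, since Protocol 8.3.1 makes the return of elevated readings to pre-dose levels a condition for ending the session. The reading before the supplement is the more informative one. It is already tabulated by session, though not by dose.

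A reader might infer that harms at 80 mg and 120 mg cannot be told apart in this trial. The documents do not support that. Every dose is recorded (Protocol 9.2.4), unanalysed data go into listings (SAP 8.0), and Session 1 is at 80 mg for everyone. A by-dose table could be made afterwards; it is simply not planned.

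It might also be argued that the reference in Protocol 14.1.2 to exposure already means dose strata. It reads more naturally as the first item in a list of safety domains, and neither document defines such strata. The wording should be clarified.

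**Conclusion.** The point holds for the planned tables. None of the four safety domains has a dose breakdown, the named stratifier has one level, and up to 120 of 180 sessions can differ in initial dose without this showing in any safety summary. These findings rest on the text alone.

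The size of any distortion is unknown, because the documents give neither event risks by dose nor an expected share on 120 mg. The illustrated 20% to 28% depends wholly on assumed values.

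This is a low-cost improvement that should be made. It does not affect the primary analysis or loss of data. A reader might infer that by-dose tables would establish how harm changes with dose. They would not, because dose was not randomised, is tied to session order and tolerability, and some cells will be small.

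**What to change.** - **SAP 8.8.2, 8.8.3 and 8.8.4:** delete treatment group and keep an overall column.
- **Session-linked data only** (Day 0 to Day 2 adverse events and medications, session C-SSRS, and session vital signs in 8.8.5): add a breakdown by session, initial dose given (80 or 120 mg) and supplement given (yes or no). Use sessions at that dose as the denominator, and in these tables count each preferred term once per session.
- **Timing:** key vital signs taken before the supplement, and adverse events starting before it, to the initial dose only. Key later ones to the initial dose plus supplement status. The documents do not say whether the time of onset is collected. If it is not, apply this split to vital signs only and classify Day 0 events by the session's initial dose and supplement status.
- **Pretreatment and follow-up adverse events:** leave as overall summaries, since they belong to no session dose.
- **SAP 8.8.1 and 8.5:** tabulate initial dose and supplement given at each session, and the dose path over the three sessions.
- **Protocol 14.1.2:** clarify what summarising by exposure means.
- **Caveat in the SAP:** state that these tables are descriptive, that dose at Sessions 2 and 3 was chosen partly on tolerability of the earlier dose, which can mask or reverse a dose difference, and that some cells will be small.

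The cost is SAP wording and some extra table columns. Doses are already logged, and neither dosing nor visits change.
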